## 9.3.3. Primary Analysis

The primary endpoint is COVID-19 related mortality during the first 28 days of follow-up. The imary endpoint will be analyzed with a Cox regression model, with plasma treatment (yes/no) and study site (stratification factor in the randomization) as covariates. A hazard ratio of plasma treatment with a 95% confidence interval will be estimated, and a test of a hazard ratio equal to one will be performed.

The survival curves for the two groups (intervention vs. control) will be estimated and plotted with the Kaplan-Meier estimator and the equality of the survival curves will be tested with the log-rank test.

The primary analysis will be performed on the FAS. A secondary analysis will be performed on the PPS.

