## **Objectives and endpoints**

Objectives	Endpoints
Primary	
Assess the effect of convalescent plasma on mortality in COVID-19	Primary endpoint: All-cause mortality within the first 28 days of observation. Secondary endpoints: All-cause mortality within 60 days of observation.
Secondary	
Effect of convalescent plasma on recovery time in patients with active COVID-19 infection	Time from intervention to negative SARS-CoV-2 PCR during a 28 days observation period.
Effect of convalescent plasma on clinical progression of COVID-19 disease	Requirement of oxygen therapy at days 1, 3, 7, 14, 21 and 28 compared to baseline. Change in NEWS score at days 1, 3, 7, 14, 21 and 28 compared to baseline.
Exploratory	
Effect of convalescent plasma on biomarkers in COVID-19	Change in CRP and lymphocyte count at day 1, 3, 7 and 14 after intervention. Time to normalized CRP and lymphocyte count.
Safety of convalescent plasma in COVID-19	Incidence of adverse events.

Brief Summary:	The objective of this study is to evaluate the safety and efficacy of convalescent plasma treatment in symptomatic elderly COVID-19 patients in Norwegian care homes. Approximately 500 eligible participants will randomly
	allocated to either the intervention (Convalescent plasma and standard care) or control (standard care only) group in a 1:1 ratio. Participants will be followed up over a 60-day observation period.
Intervention Group and Duration:	Participants randomized to treatment group will receive convalescent plasma treatment within 2 days after randomization. They will be followed up for 60 days.
Data Monitoring Committee:	Yes
Project leader	[name], Oslo University Hospital
National coordinating institution:	Oslo University Hospital
Study sites:	Study sites are defined as the care home department of participating municipalities
Study monitor:	Clinical trial unit (CTU), Oslo University Hospital
Study setting:	Norwegian care homes for elderly patients in participating municipalities
Inclusion and exclusion criteria	
 
Inclusion criteria
 
1. Age >50 years
 
2. SARS-CoV-2 PCR positive in respiratory tract sample within 3 days before inclusion
 
3. Onset of symptoms within 7 days before intervention as assessed by the attending clinician,
 
4. Voluntary, informed and documented consent by patient or guardian
 

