# **3. Objectives and Endpoints**

Objectives	Endpoints
Primary	
Assess the effect of convalescent plasma on mortality in COVID-19	Primary endpoint: All-cause mortality within the first 28 days of observation. Secondary endpoints: All-cause mortality within 60 days of observation.
Secondary	
Effect of convalescent plasma on recovery time in patients with active COVID-19 infection	Time from intervention to negative SARS-CoV-2 PCR during a 28 day observation period
Effect of convalescent plasma on clinical progression of COVID-19 disease	Requirement of oxygen therapy at days 1, 3, 7, 14, 21 and 28 compared to baseline Change in NEWS score at days 1, 3, 7, 14, 21 and 28 compared to baseline
Exploratory	
Effect of convalescent plasma on biomarkers in COVID-19	Change in CRP and lymphocyte count at day 1, 3, 7 and 14 in the study period. Time to normalized CRP and lymphocyte count
Safety of convalescent plasma in COVID-19	Incidence of adverse events

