## 6.2. Measures to Minimize Bias: Randomization and Blinding

**Sequence:** A randomization sequence will be generated in a computer program and associated with predefined rows of unique patient identification numbers and inserted into the electronic data capture system (EDCS). After the participant has consented the ambulatory team will be informed and will randomize the participant using the EDCS.

Implementation; The randomization list will be produced by the CTU at OUH.

**Blinding:** This is an open-label, randomized controlled trial with a plasma arm administered as a transfusion, and all participants and staff will thus know the intervention to which the patient is allocated.

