## 8. Study Assessments and Procedures

## 8.1. Efficacy assessments

*The efficacy of convalescent plasma on the primary endpoint of all-cause mortality* at day 28 will be recorded from the Norwegian death registry.

*The efficacy of convalescent plasma on the secondary endpoint of all-cause mortality* at day 60 will be recorded from the Norwegian death registry.

*The efficacy of convalescent plasma on the secondary endpoint of recovery time* will be assessed by repeated respiratory tract sampling for SARS-CoV-2 PCR analyses at day 1, 3, 7, 14 and 28. The site for sampling as well as the actual sampling technique will be standardized, underscoring the importance of a uniform procedure for all participating centers. Samples will be analyzed at the participating local microbial laboratories adhering to national guidelines for this testing. All samples for a single patient will be tested at the same laboratory to reduce inter-institutional variability. Samples will furthermore be stored for analyses at a core laboratory after the end of the study.

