# 9.2. Sample Size Determination

In countries with at least 100 deaths in total and data are available, the proportion of COVIDrelated deaths among care home residents ranged from 19% in Hungary to 62% in Canada; for Norway this was 61%.

The case fatality rate among COVID-19 patients in institutions outside hospitals is inconsistently reported across multiple Western countries, including Norway (https://ltcCOVID.org).

In a study from Wuhan, China with 201 COVID-19 patients the CFR was 21.9% among a population with median age 51 years (IQR 43-60)(Wu et al 2020). Others have reported CFR among COVID-19 patients aged 80 years or above in Hubei, China at 39.0% (95% KI: 31.1-48.9%) and at 89.0% (95% KI: 56.2-99.6%) in North Italy (Hauser et al 2020)

Estimates for reduction in mortality among patients receiving convalescent plasma for treatment of COVID-19 have not been found. We therefore consider several different scenarios below (Table 1 and 2).

The sample size-calculations are based on a primary outcome of time to death, to be analyzed by a Cox regression model.

We consider this to be the most realistic scenario:: To achieve 80% power to detect a difference between 30% mortality in the standard care group and 18% mortality in the convalescent plasma group (a relative reduction in mortality of 40%, which corresponds to a hazard ratio of approximately 0.60), N = 502 patients need to be recruited and 121 deaths need to be observed during the follow-up period.

There will be one interim analysis of efficacy (on the primary outcome) after half the patients have completed the first 28 days of follow-up. We will use a O'Brien and Fleming group sequential design (Wassmer&Brannath, 2016), where the interim analysis will be performed with a significance level of  $\alpha$ =0.0052, and the final analysis (after all patients have completed the

study) will be performed with a significance level of  $\alpha$ =0.048, thus maintaining an overall significance level of 5%. The inflation factor with this design is 1.008, raising the total number of patients to N = 502\*1.008 = 506. The interim analysis will be carried out on 253 patients.

	Relative reduction of mortality in the convalescent plasma group					
Mortality in the standard care group	20% #events = 631	30% #events=247	40% #events=121	50% #events=66		
20%	N = 3503	N = 1452	N = 752	N = 436		
30%	N = 2336	N = 968	N = 502	N = 291		
40%	N = 1752	N = 726	N = 376	N = 218		

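### Section 9.3.3 names COVID-19 related mortality as the primary endpoint where the rest of the protocol fixes 28-day all-cause mortality, so two different primary analyses could be run

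*Protocol*

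**What the plan says.** The protocol defines the primary endpoint in four places.

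- Synopsis (1.1), objectives table: "Primary endpoint: All-cause mortality within the first 28 days of observation".
- Section 3: "All-cause mortality within the first 28 days of observation".
- Section 8.1 describes efficacy "on the primary endpoint of all-cause mortality" and gives the source: it "at day 28 will be recorded from the Norwegian death registry".
- Section 9.3.3, which specifies the Cox model, its covariates and the test of the hazard ratio: "The primary endpoint is COVID-19 related mortality during the first 28 days of follow-up".

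Three other sections bear on the endpoint without naming a cause. Section 9.1 frames both hypotheses in terms of mortality. Section 9.2 says: "The sample size-calculations are based on a primary outcome of time to death, to be analyzed by a Cox regression model". Section 9.5 runs the interim efficacy test on the primary outcome once mortality data are in for the first 253 patients, and stops the trial if an effect is shown.

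On blinding, Section 6.2 says that "all participants and staff will thus know the intervention to which the patient is allocated".

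**The concern.** The section an analyst would implement names a different event from the sections that define the objective, the endpoint and its data source. Death from any cause and death related to COVID-19 are different sets of events, and only one of them can be primary.

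The conflict reaches both confirmatory looks, because the interim stopping decision in 9.5 rests on whatever the primary outcome is. Section 9.3 requires the SAP only before database lock, so the interim could come before any SAP that settles the matter.

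The two endpoints also differ in kind. Death from any cause, read from a registry, needs no judgement. COVID-19 related death needs a cause to be assigned in residents whom Section 5 describes as often having dementia and comorbidities. The protocol does not define such a death, say who assigns it, provide blinded adjudication, or say how other deaths enter the Cox model.

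**Working it through.** **1. The plan's own figure.** Section 9.2 gives the target: "To achieve 80% power to detect a difference between 30% mortality in the standard care group and 18% mortality in the convalescent plasma group", with a hazard ratio of about 0.60, 121 deaths and N = 502, or 506 after the interim inflation factor of 1.008.

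- Events (Schoenfeld, 1:1): D = 4(1.960 + 0.842)² / (ln 0.60)² = 120.3, rounded up to 121.
- Patients: average mortality is (0.30 + 0.18)/2 = 0.24, and 120.3/0.24 = 501.3, rounded up to 502.
- Inflation: 502 × 1.008 = 506.

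The figures reproduce.

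**2. The design with all-cause mortality throughout.** Expected deaths are 506 × 0.24 = 121.4. Power at the final level of 0.048 (critical value 1.977) is Φ(√(121.4/4) × |ln 0.60| − 1.977) = 79.9%. Correcting 9.3.3 leaves the design as it is.

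**3. How far the endpoints can differ without any bias.** The protocol does not give the share f of control deaths that are COVID-19 related, so f is an assumption. Assume also that control all-cause mortality is 30%, that plasma cuts COVID-19 deaths by 40%, and that it leaves other deaths unchanged. Then:

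- COVID-19 related events = 506 × 0.24 × f, with hazard ratio 0.60;
- all-cause mortality on plasma = 0.30 × (0.60f + 1 − f);
- the all-cause hazard ratio is approximated by the ratio of risks, as the protocol does.

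| f | COVID-19 related events | Power (HR 0.60) | All-cause HR | All-cause events | Power |
|---|---|---|---|---|---|
| 0.95 | 115.4 | 78% | 0.62 | 123.0 | 75% |
| 0.90 | 109.3 | 76% | 0.64 | 124.5 | 70% |
| 0.80 | 97.2 | 71% | 0.68 | 127.5 | 58% |
| 0.70 | 85.0 | 65% | 0.72 | 130.5 | 46% |

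The two readings give different event counts, hazard ratios and power from the same patients.

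**4. What differential attribution could do.** Assume no true effect, 30% mortality in both arms and 253 patients per arm, so 75.9 deaths per arm. Let a share of deaths in each arm be attributed to COVID-19. The apparent hazard ratio is the ratio of the shares. With E counted events, μ = √(E/4) × |ln HR|, and the two-sided error at 0.048 is Φ(μ − 1.977) + Φ(−μ − 1.977).

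| Control share | Plasma share | Counted events | Apparent HR | Two-sided error |
|---|---|---|---|---|
| 95% | 90% | 140.4 | 0.95 | 6.0% |
| 95% | 85% | 136.6 | 0.89 | 9.7% |
| 90% | 80% | 129.0 | 0.89 | 9.9% |

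For the middle row: 75.9 × 0.95 = 72.1 and 75.9 × 0.85 = 64.5, which sum to 136.6; μ = √34.15 × 0.111 = 0.65; error = 0.092 + 0.004, about 9.7%. These shares are assumptions with no basis in the protocol. They show sensitivity and do not predict what would happen.

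**The case against.** The strongest reply is that 9.3.3 is loose or leftover wording. Everyone enrolled is PCR-positive and symptomatic, the objective is mortality in COVID-19, and three sections plus the stated data source say all-cause. Section 9.3.3 itself plots ordinary survival curves. The schedule of activities lists mortality registration but no cause-of-death item, and the data condition for the interim is that mortality is known. All of this is fair, and it shows which text should prevail. It does not remove the contradiction: an analyst who follows 9.3.3 as written would count a different and undefined set of deaths.

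The reply does limit the claim. Three stronger readings are tempting and are not supported.

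- A reader might infer that unblinded staff will attribute the deaths. The protocol says that staff know the allocation; it does not say that they classify cause. The only named source is the registry.
- A reader might infer that non-COVID deaths, including transfusion-related ones, will be censored. Section 9.3.3 says nothing about censoring. How such a death in a PCR-positive resident would be classified is not stated.
- A reader might infer that the sample size rests explicitly on all-cause mortality. Section 9.2 speaks of mortality and time to death without restriction, but its background figures include case fatality rates and COVID-related deaths.

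The exclusion of residents with a life expectancy under 90 days should also reduce non-COVID deaths, though it does not make the two endpoints equal.

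**Conclusion.** The contradiction is real, stands in current text, and concerns the primary endpoint in the section that fixes the test. It must be settled before the interim efficacy look. That conclusion rests on the conflicting definitions alone and needs no assumption about bias.

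The consequences are conditional. If 9.3.3 were followed literally, some deaths might not count as events, possibly including transfusion-related ones. Attribution could then be biased, because the trial is open-label and cause is neither defined nor blindly adjudicated. The protocol gives nothing from which to size this. Under the assumed shares above, the two-sided error rises from 4.8% to between 6% and 10%. Without bias, the 9.3.3 endpoint would yield about 85 to 115 events instead of 121 if 70% to 95% of deaths are COVID-19 related.

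**What to change.** In Section 9.3.3, replace COVID-19 related mortality with all-cause mortality within the first 28 days, taken from the Norwegian death registry. In Section 9.5, state that the interim efficacy test uses this same endpoint. Carry the wording into the SAP and the DMC charter.

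The cost is one sentence in each section. The planned 506 patients and about 121 deaths do not change, and the registry is already the planned source, so no new data are needed. That last point covers this correction only: any added analysis of COVID-19 related death would need a definition and cause-of-death data that the protocol does not now provide for.

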## 9.3.4. Secondary Analyses

Secondary endpoints will be analyzed in a similar manner as the primary endpoint, with Cox regression models and Kaplan-Meier survival curve estimation – or other suitable statistical methods – as detailed in the SAP, to be completed before database lock.

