	Randomization and plasma transfusion will take place immediately after enrolment, by an ambulant transfusion team. Blood samples will be taken at day 0, 1, 3, 7 and 14 in the study period. Oropharynx samples will be taken at day 0, 1, 3, 7, 14, 21 and 28 in the study period.	

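### For time to negative PCR, the Kaplan-Meier default in Section 9.3.4 would overstate clearance if deaths are censored; separately, Section 8.1 omits the day-21 swab

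*Protocol*

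**What the plan says.** Protocol Section 9.3.4 sets the general approach: "Secondary endpoints will be analyzed in a similar manner as the primary endpoint, with Cox regression models and Kaplan-Meier survival curve estimation". The same sentence goes on to permit alternative methods, to be detailed in an SAP completed before database lock. Section 9.3 also says that the SAP will describe the analysis of every secondary endpoint.

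Section 3 lists four kinds of secondary endpoint: all-cause mortality to day 60, time from intervention to a negative SARS-CoV-2 PCR over 28 days, oxygen requirement on fixed days, and NEWS ("Change in NEWS score at days 1, 3, 7, 14, 21 and 28 compared to baseline"). The protocol does not say how a death counts in the last three.

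The planned mortality is in Section 9.2: "To achieve 80% power to detect a difference between 30% mortality in the standard care group and 18% mortality in the convalescent plasma group".

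On the swabs, Section 8.1 says that recovery time will be assessed "by repeated respiratory tract sampling for SARS-CoV-2 PCR analyses at day 1, 3, 7, 14 and 28". The synopsis (Section 1.1, participants' timeframe) says: "Oropharynx samples will be taken at day 0, 1, 3, 7, 14, 21 and 28 in the study period". The schedule of activities (Section 1.2) also marks day 21.

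**The concern.** Death removes the chance of a negative PCR. It is therefore a competing event for clearance, not ordinary loss to follow-up. If deaths are censored, one minus the Kaplan-Meier estimate (1 − KM) describes a setting in which nobody dies and the dead would have cleared at the same rate as those still under observation. Read as the proportion of patients who became negative, it is too high. It is too high by more in the arm with more deaths, so the two curves are off by different amounts if plasma lowers mortality as the trial hopes.

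The swab discrepancy bears on the same endpoint. Clearance is seen only on swab days. If Section 8.1 governs the analysis, any clearance after day 14 is first seen at day 28, although a day-21 sample will have been taken.

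**Working it through.** **The plan's own figures.** Section 9.2 gives 30% versus 18% mortality, a hazard ratio of about 0.60, 80% power and an overall 5% level, taken here as two-sided. Allocation is 1:1 (Section 9.3.1). Schoenfeld's formula gives

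events = 4 × (1.960 + 0.842)² / (ln 0.60)² = 120.3, rounded up to 121.

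Dividing 120.3 by the mean mortality of 0.24 gives 501.3, rounded up to 502, and 502 × 1.008 = 506.0. This agrees with the protocol: "N = 502 patients need to be recruited and 121 deaths need to be observed during the follow-up period", then 506 after inflation. With 253 patients per arm, the design expects 253 × 0.30 = 75.9 deaths in control and 253 × 0.18 = 45.5 in plasma. I read these rates as 28-day mortality because that is the primary endpoint.

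**Assumptions for the check.** The protocol gives no clearance rate. I assume constant hazards, independence of death and clearance, no plasma effect on clearance, and a net 28-day clearance c (the value if nobody died) of 50%, 70% or 90%. The death hazards are set from the two mortality figures m.

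**Formulas.** With λc = −ln(1 − c)/28 and λd = −ln(1 − m)/28:

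- 1 − KM at day 28, deaths censored, equals c in both arms.
- Cumulative incidence at day 28 = λc/(λc + λd) × [1 − (1 − c)(1 − m)].

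**Worked case, c = 70%.**

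- Control: 1.204/(1.204 + 0.357) × (1 − 0.30 × 0.70) = 0.7715 × 0.790 = 60.9%.
- Plasma: 1.204/(1.204 + 0.198) × (1 − 0.30 × 0.82) = 0.8585 × 0.754 = 64.7%.

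| 1 − KM, both arms | Cumulative incidence, control | Cumulative incidence, plasma | Overstatement, control | Overstatement, plasma |
|---|---|---|---|---|
| 50% | 42.9% | 45.9% | 7.1 points | 4.1 points |
| 70% | 60.9% | 64.7% | 9.1 points | 5.3 points |
| 90% | 80.5% | 84.5% | 9.5 points | 5.5 points |

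The actual proportions cleared differ by 3 to 4 points between arms, purely because of mortality. The Kaplan-Meier curves show no difference.

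**The Cox model.** This was simulated with 100,000 patients per arm, the model fitted to a random 20,000 of them, net clearance of 70% and no plasma effect on clearance. With deaths censored, the hazard ratio is 0.99 (SE 0.02) when death and clearance are independent. It is also 0.99 with a shared frailty of log-SD 0.7, and about 0.95 with log-SD 1.0 or 1.5. The frailty values are assumptions.

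**The swab days.** Section 8.1 lists 1, 3, 7, 14 and 28. The synopsis and the schedule list 0, 1, 3, 7, 14, 21 and 28. Without day 21 the last interval is 28 − 14 = 14 days; with it, there are two intervals of 7 days.

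**The case against.** The strongest reply is that Section 9.3.4 does not fix Cox and Kaplan-Meier for every secondary endpoint. It allows other suitable methods, and the SAP, which is not at hand, may already treat death as a competing event. That stands. A reader might infer that the plan commits itself to censoring deaths or treating them as missing, but no section says so.

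Three further limits also stand.

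- Cox regression with deaths censored estimates a legitimate cause-specific hazard ratio. A reader might infer that plasma would look worse on clearance because it saves lives. In the check, that happens only under strong assumed frailty, and the shift is then only to about 0.95.
- Cox and Kaplan-Meier are right for 60-day mortality, where death is the event.
- Oxygen and NEWS are measured on fixed days, so they fall naturally under the clause that allows other methods. A reader might infer that they will be compared in survivors only. The protocol does not say that, and the handling of death there is commonly left to the SAP. A count of how many more plasma patients would enter a NEWS comparison cannot be given either, because NEWS is recorded only in care homes that already use it (Section 1.2).

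Fine-Gray regression, or ranking death as the worst outcome, is a choice of estimand on which statisticians differ. With no plasma effect on clearance, keeping the dead at risk as not cleared gave a hazard ratio of about 1.05 to 1.09 in the same simulation, so that measure carries the mortality effect with it.

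The reply leaves one thing untouched: for PCR clearance, Kaplan-Meier is the named default, and a better curve is available at no cost.

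**Conclusion.** The point holds in a limited form. For time to negative PCR, a Kaplan-Meier curve with deaths censored should not be read as the proportion cleared. At the planned mortality it would overstate that proportion by about 7 to 10 points in control and 4 to 6 in plasma. This rests on constant hazards, independence of death and clearance, no plasma effect on clearance and an assumed net clearance of 50% to 90%. It is an improvement to the named default, not a demonstrated error in the final analysis, and no sample-size figure changes.

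The omission of day 21 from Section 8.1 is a plain inconsistency and depends on none of these assumptions. The handling of death for oxygen and NEWS is a suggestion for the SAP only.

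**What to change.** - **Section 9.3.4.** For time to negative PCR, replace the Kaplan-Meier curve with cumulative incidence, death being a competing event. Keep the Cox model and label its result a cause-specific hazard ratio. Keep Cox and Kaplan-Meier for 60-day mortality.
- **Section 8.1.** Reconcile the swab days with the synopsis and the schedule of activities so that the day-21 sample counts in the endpoint.
- **SAP (suggestion).** State how death is handled for oxygen and NEWS.

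The cost is a few sentences; no data are added, because the day-21 swab is already scheduled. The one downside is that cumulative incidence reflects mortality as well as clearance. It should therefore be reported beside the cause-specific hazard ratio, so that a reader can see which of the two drives a difference.
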